10.3.1. Definition of AE

AE Definition

- An AE is any untoward medical occurrence in a clinical study participant, temporally associated with the use of a study intervention, whether or not considered related to the study intervention.
- NOTE: An AE can therefore be any unfavorable and unintended sign (including an abnormal laboratory finding), symptom, or disease (new or exacerbated) temporally associated with the use of a study intervention.

Events Meeting the AE Definition

- Any abnormal laboratory test results (hematology, clinical chemistry, or urinalysis) or other safety assessments (e.g., ECG, radiological scans, vital signs measurements), including those that worsen from baseline, considered clinically significant in the medical and scientific judgment of the investigator (i.e., not related to progression of underlying disease).
- Exacerbation of a chronic or intermittent pre-existing condition including either an increase in frequency and/or intensity of the condition.
- New conditions detected or diagnosed after study intervention administration even though it may have been present before the start of the study.
- Signs, symptoms, or the clinical sequelae of a suspected drug-drug interaction.
- Signs, symptoms, or the clinical sequelae of a suspected overdose of either study intervention or a concomitant medication. Overdose per se will not be reported as an AE/SAE unless it is an intentional overdose taken with possible suicidal/self-harming intent. Such overdoses should be reported regardless of sequelae.
- "Lack of efficacy" or "failure of expected pharmacological action" per se will not be reported as an AE or SAE. Such instances will be captured in the efficacy assessments. However, the signs, symptoms, and/or clinical sequelae resulting from lack of efficacy will be reported as AE or SAE if they fulfill the definition of an AE or SAE.

Events NOT Meeting the AE Definition

- Any clinically significant abnormal laboratory findings or other abnormal safety assessments which are associated with the underlying disease, unless judged by the investigator to be more severe than expected for the participant's condition.
- The disease/disorder being studied or expected progression, signs, or symptoms

- of the disease/disorder being studied, unless more severe than expected for the participant's condition.
- Medical or surgical procedure (e.g., endoscopy, appendectomy): the condition that leads to the procedure is the AE.
- Situations in which an untoward medical occurrence did not occur (social and/or convenience admission to a hospital).
- Anticipated day-to-day fluctuations of pre-existing disease(s) or condition(s) present or detected at the start of the study that do not worsen.

10.3.2. Definition of SAE

If an event is not an AE per definition above, then it cannot be an SAE even if serious conditions are met (e.g., hospitalization for signs/symptoms of the disease under study, death due to progression of disease).

A SAE is defined as any untoward medical occurrence that, at any dose:

- o Results in death
- o Is life-threatening

The term 'life-threatening' in the definition of 'serious' refers to an event in which the participant was at risk of death at the time of the event. It does not refer to an event, which hypothetically might have caused death, if it were more severe.

Requires inpatient hospitalization or prolongation of existing hospitalization

- In general, hospitalization signifies that the participant has been detained (usually involving at least an overnight stay) at the hospital or emergency ward for observation and/or treatment that would not have been appropriate in the physician's office or outpatient setting. Complications that occur during hospitalization are AE. If a complication prolongs hospitalization or fulfills any other serious criteria, the event is serious. When in doubt as to whether "hospitalization" occurred or was necessary, the AE should be considered serious.
- Hospitalization for elective treatment of a pre-existing condition that did not worsen from baseline is not considered an AE.

Results in persistent or significant disability/incapacity

- The term disability means a substantial disruption of a person's ability to conduct normal life functions.
- This definition is not intended to include experiences of relatively minor medical significance such as uncomplicated headache, nausea, vomiting, diarrhea, influenza, and accidental trauma (e.g. sprained ankle) which may interfere with or prevent everyday life functions but do not constitute a substantial disruption.

Is a congenital anomaly/birth defect

Other situations:

- Medical or scientific judgment should be exercised in deciding whether SAE
 reporting is appropriate in other situations such as important medical events that
 may not be immediately life-threatening or result in death or hospitalization but
 may jeopardize the participant or may require medical or surgical intervention to
 prevent one of the other outcomes listed in the above definition. These events
 should usually be considered serious.
- Examples of such events include invasive or malignant cancers, intensive treatment in an emergency room or at home for allergic bronchospasm, blood dyscrasias or convulsions that do not result in hospitalization, or development of drug dependency or drug abuse.

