2.3.1. Risk Assessment

Risks are summarized in Table 5. Additional withdrawal/stopping criteria for liver chemistry monitoring, drug induced vascular injury (DIVI), hematology, renal function, and PK are discussed in Section 7. Planned dose adjustments for individuals for safety are outlined in Section 6.6.

Table 5 Summary of Potential Risks of Clinical Significance

Potential Risk of Clinical Significance	Summary of Data/Rationale for Risk	Mitigation Strategy					
Investigational Product (IP) [e.g., GSK3228836]							
Nonclinical Risks:	Inflammatory and immune changes are recognized as a	Laboratory Evaluations: Inclusion of biomarker panels to					
Drug Induced Vascular Inflammation and Complement Activation	class effect of antisense oligonucleotide (ASOs). Vasculitis and/or perivascular inflammation has been described in monkey studies with many if not most ASOs.	look for inflammatory and immune activation that would be expected to accompany vascular injury					
	This effect has not been observed in clinical studies with GSK3228836 to date.	Stopping Criteria: Proposed Monitoring Schedule and Stopping Rules for Drug Induced Vascular Injury and Complement Activation (see Section 7.1.2)					
Clinical Risks:	•						
Drug induced liver injury / ALT Flares	The liver is a site of accumulation of antisense oligonucleotides. Liver findings in nonclinical studies of GSK3228836 were generally limited to mild hepatic enzyme elevations associated with hepatic vacuolation without concomitant histologic evidence of degeneration in mice, consistent with findings noted with other 2'-methoxyethyl (MOE) ASOs. Review of the available clinical data indicates liver enzymes are increased on treatment with ASOs in a low percentage of patients compared to placebo. ALT elevations (defined as ALT ≥ 2X ULN) associated with HBsAg reductions were observed in 8 out of 18 treatment-naïve participants in the ISIS 505358-CS3 study (150 mg GSK3228836, N=6; 300 mg GSK3228836, N=12). Among the 8 participants with ALT flares, 6 achieved >1 log HBsAg reduction, another 2 had >0.5 log HBsAg reduction.	Laboratory Evaluations: hepatic enzyme monitoring as presented in Table 6 Stopping Criteria: ALT flares are expected in the study population. Monitoring and stopping criteria are presented in Section 7.1.1					

Potential Risk of Clinical Significance	Summary of Data/Rationale for Risk	Mitigation Strategy

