- 2. Urine testing will be standard for the protocol unless serum testing is required by local regulation or IRB/IEC or if urine testing is unavailable
- 3. Details of liver chemistry stopping criteria and required actions and follow-up assessments after liver stopping or monitoring event are given in Section 7.1 and Appendix 7. All events of ALT ≥3 × upper limit of normal (ULN) and bilirubin >2 × ULN (>35% direct bilirubin) or ALT ≥3 × ULN and international normalized ratio (INR) >1.5, if INR measured, which may indicate severe liver injury (possible Hy's Law), must be reported as an SAE (excluding studies of hepatic impairment or cirrhosis).

10.3. Appendix 3: Adverse Events: Definitions and Procedures for Recording, Evaluating, Follow-up, and Reporting

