4.5.2.1. Adverse Events of Special Interest

The following AEs of special interest will be reported:

- ALT increase
- Vascular inflammation and complement activation
- Thrombocytopenia
- Renal injury
- Injection site reactions

An up to date list of specific MedDRA Queries (SMQs), high level terms (HLTs) or individual preferred terms (PTs) used to identify AESIs is periodically updated and stored in a central location. At the time of DBR, the latest version of the terms will be extracted and used to identify AESIs.

All AEs of special interest will be summarized by SOC and PT, and also summarized by SOC, PT and maximum grade. Serious AESIs will be summarized by SOC and PT. All AEs of special interest will be listed.

Separate outputs will be created for each AESI category (ALT increase, vascular inflammation and complement activation, thrombocytopenia, renal injury and injection site reactions) to explore the data in more detail if data permits.

Event Characteristics: The characteristics of all event occurrences during the post-baseline period will be summarized, which looks at event characteristics (serious, drug-related, leading to withdrawal, severe or Grade 3-4, fatal), number of events per participant, outcome, maximum grade or intensity and action taken.

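### Appendix 3 and Section 8.2.5 let an unblinded investigator leave an HBV-attributed ALT flare out of AE and SAE reporting, in conflict with Table 13 note 3, the AESI section and Appendix 3's own exacerbation rule

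*Protocol*

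**What the plan says.** **Exclusion.** Protocol 10.3.1 lists among events that are not AEs "Any clinically significant abnormal laboratory findings or other abnormal safety assessments which are associated with the underlying disease", with the exception "unless judged by the investigator to be more severe than expected for the participant's condition". Expected signs or symptoms of the disease under study are excluded in a similar way. Section 8.2.5 repeats the laboratory exclusion and its exception in the body of the protocol.

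**SAE rule.** Protocol 10.3.2 states: "If an event is not an AE per definition above, then it cannot be an SAE even if serious conditions are met". Its examples are "hospitalization for signs/symptoms of the disease under study, death due to progression of disease".

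**Rules pointing the other way.**
- The AE list in 10.3.1 includes "Exacerbation of a chronic or intermittent pre-existing condition including either an increase in frequency and/or intensity of the condition".
- Table 13 note 3 (Protocol 10.2) says that all events of ALT ≥3x ULN with bilirubin >2x ULN (>35% direct), or with INR >1.5 if measured, "must be reported as an SAE (excluding studies of hepatic impairment or cirrhosis"). It sets no condition on attribution.
- Section 8.3.7.1 lists ALT increases as an AE of special interest.

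**Context.** Table 5 names drug-induced liver injury and ALT flares as a clinical risk of the product and adds that "ALT flares are expected in the study population". Section 6.3 leaves investigators unblinded throughout.

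**Analysis.** SAP 4.5.2.1 identifies AESIs from MedDRA queries and terms, and says "All AEs of special interest will be summarized by SOC and PT, and also summarized by SOC, PT and maximum grade". SAP 4.5.3.1 separately summarises and lists liver monitoring and stopping events.

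**The concern.** The same flare can fall under a rule that says it must be an SAE and a rule that says it cannot be one. Which rule a site follows turns on whether the investigator attributes the flare to HBV and regards its severity as expected. The protocol defines no expected severity. Section 8.3.7.1 concedes that, outside reactivation or rebound viraemia, the cause of flares is uncertain. The person making the call knows the arm. Section 4.2.1 accepts unblinded sites because the primary endpoint is an objective laboratory measure, and that reasoning does not extend to classifying adverse events.

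Two things are at stake. An event meeting note 3 could miss the SAE route with its 24-hour limit (8.3.1). The ALT-increase AESI tables, which carry seriousness, relatedness, outcome and action taken, would also depend on unblinded attribution.

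**Working it through.** No figure in the plan is in dispute, so the check sets the passages against three cases. In each, the investigator attributes the flare to HBV and does not consider it more severe than expected.

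**Case A: ALT ≥3x ULN with bilirubin >2x ULN (>35% direct), participant admitted.**

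| Source | Result |
|---|---|
| 10.3.1 exclusions; 8.2.5 for the laboratory finding | Not an AE |
| 10.3.1, exacerbation bullet | AE |
| 10.3.2 | If not an AE, cannot be an SAE; admission for the disease is an example |
| Table 13 note 3 | SAE. Its carve-out for hepatic impairment or cirrhosis studies does not apply, since 5.2 excludes cirrhosis |
| 8.3.7.1 | AESI |
| 7.1.1, Table 6 | Last row met: Liver Event CRF, and Medical Monitor told within 24 hours |
| SAP 4.5.2.1 | In the AESI tables only if entered as an AE |
| SAP 4.5.3.1 | In the liver-event summary and listing either way |

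The first four rows cannot all be followed, and nothing says which prevails.

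**Case B: ALT ≥3x ULN with new hepatitis symptoms, bilirubin and INR normal, participant admitted.** Note 3 does not apply. The last row of Table 6 does, so the Liver Event CRF is completed and the symptoms go on the AE CRF as relevant (7.1.1). Whether the admission is an SAE again depends on choosing between the exclusion and the exacerbation bullet in 10.3.1.

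**Case C: isolated ALT of 5x ULN, no other finding.** Neither note 3 nor Table 6 applies, because the ALT-only rows of Table 6 start at 10x ULN. The value appears in the laboratory tables. It reaches the AESI tables only if the investigator records an AE.

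**Scale.** Table 5 reports ALT ≥2x ULN in 8 of 18 treatment-naive participants in the earlier study (8/18 = 44%), so flares are not rare. The documents give no share that would be attributed to HBV and left unrecorded, so the number of misclassified events cannot be derived.

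**The case against.** The strongest reply is that Appendix 3, read as a whole, already points towards reporting. Events more severe than expected stay AEs, and exacerbation of a chronic condition is an AE. An admitted flare, or one meeting possible Hy's Law criteria, could qualify under either. Table 5 lists flares as a risk of the product, so their being expected on drug need not make them expected disease. Section 6.5.3 says only that flares may follow the end of dosing.

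Existing capture is also substantial. Table 6 events trigger the Liver Event CRF and notice to the Medical Monitor within 24 hours. SAP 4.5.3.1 summarises them and gives a profile for each participant meeting hold or stopping criteria. Both note 3 combinations fall within the last row of Table 6, so they would come to attention even if not classed as SAEs.

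These arguments limit the point but do not remove it. They show that a careful investigator could report the flare, not that the text requires it. A Liver Event CRF and a call to the Medical Monitor are not an SAE report, and the liver-event summaries do not feed the AESI tables.

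A reader might contrast ALT increases with injection site reactions, which sites are expressly told to report as AEs (8.2.2, 8.3.7.5). Little can be built on that, because the sections on vascular inflammation, thrombocytopenia and renal injury (8.3.7.2 to 8.3.7.4) also lack such a sentence.

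**Conclusion.** The conflict stands. As written, the protocol permits an unblinded investigator to leave an HBV-attributed flare, including a hospitalised one, out of AE and SAE reporting unless it is judged more severe than expected. For the note 3 subset this contradicts a mandatory rule. For the rest it leaves AESI classification to attribution. The loss is one of classification; ALT values and Table 6 events remain available.

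Three stronger readings are tempting and not supported.
- A reader might infer that Appendix 3 removes all HBV-attributed flares from reporting. It does not: the severity exception and the exacerbation bullet both leave reporting open.
- A reader might project a count of lost events from the earlier study's 33% with ALT ≥3x ULN (4.2.1). Those rises came within 4 weeks of dosing and without bilirubin or INR changes, so they say nothing about note 3 events, and no attribution share is given.
- A reader might infer that misclassified flares would bias regimen selection. SAP 4.3.1.2 selects regimens on SVR alone.

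The conclusion rests on the wording and on one assumption: that some sites will apply the exclusion literally. Because a required SAE could go unreported and the repair is small, the passages should be reconciled.

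**What to change.** - **Protocol 10.3.1, 10.3.2 and 8.2.5:** state that the underlying-disease exclusion does not apply to Table 13 note 3 events, to events meeting any row of Table 6, or to clinical hepatitis flares. These are recorded as AEs whatever the attributed cause, and as SAEs when a seriousness criterion or note 3 is met.
- **Protocol 10.3.2:** state that the hospitalisation example does not cover hepatitis flares.
- **SAP 4.5.2.1:** cross-check the ALT-increase AESI list against the liver events in SAP 4.5.3.1 and report any that have no matching AE record.

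This would not bring in isolated ALT rises below 10x ULN (Case C). Those would still rest on the investigator's judgement and be visible in the laboratory tables; the SAP should say so where it presents the ALT AESI.

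The cost is a few sentences in the protocol and one or two in the SAP, more AE and SAE records, and a higher reported hepatic event rate. The change concerns reporting only; treatment and monitoring rules are untouched.

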10.3.3. Definition of Cardiovascular Events

Cardiovascular Events (CV) Definition:

Investigators will be required to fill out the specific CV event page of the CRF for the following AEs and SAEs:

- Myocardial infarction/unstable angina
- Congestive heart failure
- Arrhythmias
- Valvulopathy
- Pulmonary hypertension
- Cerebrovascular events/stroke and transient ischemic attack
- Peripheral arterial thromboembolism
- Deep venous thrombosis/pulmonary embolism
- Revascularization

10.3.4. Recording and Follow-Up of AE and SAE

AE and SAE Recording

- When an AE/SAE occurs, it is the responsibility of the investigator to review all documentation (e.g. hospital progress notes, laboratory, and diagnostics reports) related to the event.
- The investigator will then record all relevant AE/SAE information in the CRF.
- It is **not** acceptable for the investigator to send photocopies of the participant's

medical records to GSK in lieu of completion of the GSK /AE/SAE CRF page.

- There may be instances when copies of medical records for certain cases are requested by GSK. In this case, all participant identifiers, with the exception of the participant number, will be redacted on the copies of the medical records before submission to GSK.
- The investigator will attempt to establish a diagnosis of the event based on signs, symptoms, and/or other clinical information. Whenever possible, the diagnosis (not the individual signs/symptoms) will be documented as the AE/SAE.

Assessment of Intensity

The investigator will assess intensity for each AE and SAE reported during the study and assign it to 1 of the following categories:

- Mild: An event that is easily tolerated by the participant, causing minimal discomfort and not interfering with everyday activities.
- Moderate: An event that causes sufficient discomfort and interferes with normal everyday activities.
- Severe: An event that prevents normal everyday activities. An AE that is
 assessed as severe should not be confused with an SAE. Severe is a category
 utilized for rating the intensity of an event; and both AE and SAE can be
 assessed as severe.

An event is defined as 'serious' when it meets at least 1 of the predefined outcomes as described in the definition of an SAE, NOT when it is rated as severe.

10.3.5. Division of AIDS (DAIDS) Table for Grading Severity of Adult and Pediatric Adverse Events

The DAIDS Table [DAIDS, 2017] will be used to grade the severity of an AE that is not specifically identified in the grading table. In addition, are to be classified as grade 5.

The DAIDS Table is available at the following link:

https://rsc.niaid.nih.gov/clinical-research-sites/grading-severity-adult-pediatric-adverseevents-corrected-version-two-one

Assessment of Causality

- The investigator is obligated to assess the relationship between study intervention and each occurrence of each AE/SAE.
- A "reasonable possibility" of a relationship conveys that there are facts, evidence, and/or arguments to suggest a causal relationship, rather than a relationship cannot be ruled out.
- The investigator will use clinical judgment to determine the relationship.

- Alternative causes, such as underlying disease(s), concomitant therapy, and other risk factors, as well as the temporal relationship of the event to study intervention administration will be considered and investigated.
- The investigator will also consult the Investigator's Brochure (IB) and/or Product Information, for marketed products, in his/her assessment.
- For each AE/SAE, the investigator must document in the medical notes that he/she has reviewed the AE/SAE and has provided an assessment of causality.
- There may be situations in which an SAE has occurred and the investigator has minimal information to include in the initial report to GSK. However, it is very important that the investigator always make an assessment of causality for every event before the initial transmission of the SAE data to GSK.
- The investigator may change his/her opinion of causality in light of follow-up information and send an SAE follow-up report with the updated causality assessment.
- The causality assessment is one of the criteria used when determining regulatory reporting requirements.

10.3.6. Reporting of SAE to GSK

SAE Reporting to GSK via Electronic Data Collection Tool

- The primary mechanism for reporting SAE to GSK will be the electronic data collection tool.
- If the electronic system is unavailable, then the site will use the paper SAE data collection tool (see next Section) in order to report the event within 24 hours.
- The site will enter the SAE data into the electronic system as soon as it becomes available.
- The investigator or medically-qualified sub-investigator must show evidence within the eCRF of review and verification of the relationship of each SAE to IP/study participation (causality) within 72 hours of SAE entry into the eCRF.
- After the study is completed at a given site, the electronic data collection tool will be taken off-line to prevent the entry of new data or changes to existing data.
- If a site receives a report of a new SAE from a study participant or receives updated data on a previously reported SAE after the electronic data collection tool has been taken off-line, then the site can report this information on a paper SAE form (see next Section) or to the Medical Monitor by telephone.
- Contacts for SAE reporting can be found in the SRM.

SAE Reporting to GSK via Paper CRF

- Facsimile transmission of the SAE paper CRF is the preferred method to transmit this information to the Medical Monitor.
- In rare circumstances and in the absence of facsimile equipment, notification by telephone is acceptable with a copy of the SAE data collection tool sent by overnight mail or courier service.
- Initial notification via telephone does not replace the need for the investigator to complete and sign the SAE CRF pages within the designated reporting time frames.
- Contacts for SAE reporting can be found in the SRM.

